### 12.5 Sample Size Considerations

Five patients with EoE-CTD and 10 patients with EoE will be recruited into the study. Since this represents a pilot study to evaluate whether the treatment affects endpoints, the sample size was not selected on the basis of power considerations for statistical testing. The estimates of treatment effect from this study will be used to power future studies. Based on historical data from the [REDACTED], it is estimated that the standard deviation of the change from baseline at 12 weeks based on the square root transformation of the eosinophil/HPF values will be approximately 5. Table 7 provides the width of the two-sided 95% confidence interval for the change from baseline in eosinophil/HPF for various scenarios of sample size and standard deviation.

12.5.1 Table 7: Standard Deviation and Confidence Interval Widths

Sample Size	Standard Deviation (square root transform)	Width of Confidence Interval (square root transform)
15 (both groups combined)	5	$\pm 2.8$
	10	$\pm 5.5$
10 (EoE)	5	$\pm 3.6$
	10	$\pm 7.2$
5 (EoE-CTD)	5	$\pm 6.2$
	10	$\pm 12.4$

For binary endpoints (e.g. percentage of participates for whom peak eosinophil counts are < 15 eosinophil/HPF), the following table provides the width of the two-sided 95% confidence interval for the binary endpoint given various scenarios of response rates (Table 8).

**12.5.2 Table 8: 95% Two-sided Score Confidence Interval**

Sample Size	Response Rate	Estimated Confidence Interval
15 (both groups combined)	80%	55% to 93%
	60%	36% to 80%
	40%	28% to 64%
10 (EoE)	80%	49% to 94%
	60%	31% to 83%
	40%	17% to 69%
5 (EoE-CTD)	80%	38% to 96%
	60%	23% to 88%
	40%	12% to 77%
See Reference (81)		

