For testing consistency of the time trend ( $\beta$ ) between the CTD and non-CTD group, the hypotheses are:

$H_0: \beta_{EoE-CTD} = \beta_{EoE(non-CTD)}$  vs.  $H_1: \beta_{EoE-CTD} \neq \beta_{EoE(non-CTD)}$ .

For testing linear trend combining across groups (if there is consistency of the time trend):

$H_0: \beta=0$  vs.  $H_1: \beta \neq 0$

where  $\beta$  is the slope of the line across groups. Similar hypotheses will be tested if analysis of the residuals indicates that higher order terms need to be included in the model (e.g. quadratic). If there is strong evidence that the time trend is not consistent between the two groups, we will test the above hypothesis within each of the two groups. In addition, the two-sided, 95% confidence interval for the slopes will be calculated to provide estimates of the slope for future studies.

The percentage of participants for whom peak eosinophil counts are  $< 15$  eosinophil/HPF at Week 16 will be estimated within each CTD group along with a 95% confidence interval.

Safety endpoints that are categorical will be summarized within each group. Further, any SAEs or Grade 3 or above will be reported descriptively.

All analyses will be performed using SAS version 9.2 or later (Cary, NC).

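### Protocol Table 8, 15 participants at a 40% response: the lower limit reads 28%, but the 95% score interval for 6/15 is 20% to 64%; check the source page, then correct.

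*Protocol*

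**What the plan says.** Protocol section 12.5 fixes the numbers: "Five patients with EoE-CTD and 10 patients with EoE will be recruited into the study". It adds that "the sample size was not selected on the basis of power considerations for statistical testing". In place of a power calculation it offers two precision tables. Table 7 covers the change in square-root eosinophil count. Table 8 covers binary endpoints, with the percentage below 15 eosinophils/HPF as the example, and is introduced by the sentence "the following table provides the width of the two-sided 95% confidence interval for the binary endpoint given various scenarios of response rates".

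Table 8 is headed "Table 8: 95% Two-sided Score Confidence Interval". It has three sample sizes (15 combined, 10 EoE, 5 EoE-CTD) and three response rates (80%, 60%, 40%). For 15 participants it prints 55% to 93%, 36% to 80%, and 28% to 64%.

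For the analysis itself, Protocol section 12.4 says the responder percentage "at Week 16 will be estimated within each CTD group along with a 95% confidence interval". The SAP, under Analyses of Secondary Endpoint(s)/Outcome(s), says the same and does not repeat Table 8.

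**The concern.** The 40% row for 15 participants is out of line with the row above it. At a fixed sample size, the score interval for a 40% response is the mirror image of the one for 60%, and the two have the same width. The 60% row is 80 − 36 = 44 points wide, while the 40% row is 64 − 28 = 36 points wide.

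Because the trial was not sized on power, Tables 7 and 8 are the protocol's only quantitative statement of what 15 participants can deliver. As printed, the row says that an observed 40% response would exclude true rates below 28%. With the correct limit it excludes only rates below about 20%. The error therefore overstates precision.

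**Working it through.** **Inputs** (all from Protocol Table 8): two-sided 95% score interval; n = 15; response rate 40%, so x = 0.40 × 15 = 6. z = 1.960, z² = 3.841.

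**Formula** (Wilson score interval, no continuity correction):

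limits = [p + z²/(2n) ± z·√(p(1 − p)/n + z²/(4n²))] / (1 + z²/n)

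**Step 1. Confirm the method on the whole table.** Limits in percent:

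| n | x (rate) | Printed | Computed |
|---|---|---|---|
| 15 | 12 (80%) | 55–93 | 54.81–92.95 |
| 15 | 9 (60%) | 36–80 | 35.75–80.18 |
| 15 | 6 (40%) | **28**–64 | **19.82**–64.25 |
| 10 | 8 (80%) | 49–94 | 49.02–94.33 |
| 10 | 6 (60%) | 31–83 | 31.27–83.18 |
| 10 | 4 (40%) | 17–69 | 16.82–68.73 |
| 5 | 4 (80%) | 38–96 | 37.55–96.38 |
| 5 | 3 (60%) | 23–88 | 23.07–88.24 |
| 5 | 2 (40%) | 12–77 | 11.76–76.93 |

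Seventeen of the 18 printed limits reproduce to the whole percent, so this is the formula the table used.

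**Step 2. The disputed row in full.**

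- z²/n = 3.841/15 = 0.2561, so the denominator is 1.2561.
- Centre: (0.40 + 0.1280)/1.2561 = 0.4204.
- Half-width: 1.960 × √(0.24/15 + 3.841/900)/1.2561 = 1.960 × √(0.01600 + 0.00427)/1.2561 = 1.960 × 0.1424/1.2561 = 0.2221.
- Limits: 0.4204 − 0.2221 = 0.198 and 0.4204 + 0.2221 = 0.643 (0.6425 before rounding).

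Rounded, this is 20% to 64%.

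**Step 3. Mirror check, using printed figures only.** Subtract each 60% row from 100 to get the 40% row.

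- n = 10: 31–83 gives 17–69, as printed.
- n = 5: 23–88 gives 12–77, as printed.
- n = 15: 36–80 gives 20–64; the table has 28–64.

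**Step 4. Could another reading give 28% to 64%?** For 6/15 at 95%:

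| Method | Interval (%) |
|---|---|
| Continuity-corrected score | 17.5–67.1 |
| Agresti-Coull | 19.8–64.3 |
| Clopper-Pearson (exact) | 16.3–67.7 |
| Wald | 15.2–64.8 |
| Jeffreys | 18.8–64.7 |

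Lower confidence levels do not give it either: the score interval is 22.3–60.7 at 90% and 25.6–56.4 at 80%. Nor do neighbouring counts at 95%: 5/15 gives 15.2–58.3, 7/15 gives 24.8–69.9, and 8/15 gives 30.1–75.2. At a 40% response, the smallest n whose lower score limit rounds to 28% is 50, and there the upper limit is 53.8%. None of these readings yields the printed pair.

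**Step 5. Size.** Lower limit: 28 − 19.8 = 8.2 points too high. Width: 36 points printed, 64.25 − 19.82 = 44.4 points computed.

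**The case against.** The strongest objection concerns where the figure comes from. It is one digit in a table read from a PDF by a program, and the surrounding text has other character-level faults that may come from that reading. The rest of the table was evidently computed correctly, so a lone 28 where 20 belongs is just what a 0 read as an 8 would look like. An author's slip would look the same, and the text alone cannot tell them apart. This stands, and it is why the correction depends on a look at the source page.

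The second objection is that nothing turns on the entry. The responder percentage is to be estimated within each CTD group, which corresponds to the 10- and 5-participant rows, and all six are correct. No responder interval for the combined 15 is planned. The primary endpoint is the change in peak eosinophil count, whose precision is in Table 7, and that table is not in question. The 60% row directly above the entry shows the true width of about 44 points. This also stands. It limits the point to a minor correction but does not make the entry right: Table 8 presents it as the precision available from 15 participants.

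**Conclusion.** As the text reads, the entry is wrong. The 95% score interval for 6/15 is 20% to 64%, not 28% to 64%. One of 18 printed limits is affected, by about 8 points, and it understates the width of that interval by about the same amount.

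The arithmetic rests only on the method, sample size and response rate stated in Table 8, and the table's own 60% row confirms it. The one open assumption is that the 28% is in the protocol itself and did not arise when the PDF was read. If the source page shows 20%, there is no error. In either case the sample size, the planned analyses and the trial's final intervals are unaffected, and the severity is minor.

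**What to change.** Check the lower limit of the 15-participant, 40% row of Table 8 on the source page of the protocol. If it reads 28%, change the entry to 20% to 64%. No other entry in Table 8 needs changing, and the SAP needs no edit because it does not carry the table. The cost is one number in the protocol, with no effect on sample size or analysis.

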### 13 Identification and Access to Source Data

#### 1. Source Data

Source documents and source data are considered to be the original documentation in which participant information, visits, consultations, examinations, and other information are recorded. Documentation of source data is necessary for the reconstruction, evaluation, and validation of clinical findings, observations, and other activities during a clinical trial. This will include instruments to evaluate participant symptoms, quality of life, and histologic score of esophageal biopsy samples.

#### 2. Access to Source Data

The site investigators and site staff will make all source data available to the DAIT/NIAID, the Sponsor, DSMB, and IRBs as needed. Authorized representatives as noted above are legally and ethically bound to maintain the strict confidentiality of medical and research information that may be linked to identified individuals.

## 14 Protocol Deviations

### 1. Protocol Deviation Definitions

#### Protocol Deviation

The investigators and site staff will conduct the study in accordance to the protocol; no deviations from the protocol are permitted. Any change, divergence, or departure from the study design or procedures constitutes a protocol deviation. As a result of any deviation, corrective actions will be developed by the site and implemented promptly.

#### Major Protocol Deviation (Protocol Violation)

A Protocol Violation is a deviation from the IRB-approved protocol that may affect the participant's rights, safety, or well-being and/or the completeness, accuracy, and reliability of the study data. In addition, protocol violations include willful or knowing breaches of human subject protection regulations or policies, any action that is inconsistent with the NIH Human Research Protection Program's research, medical, and ethical principles, and a serious or continuing noncompliance with federal, state, local, or institutional human subject protection regulations, policies, or procedures.

#### Non-Major Protocol Deviation

A non-major protocol deviation is any change, divergence, or departure from the study design or procedures of a research protocol that does not have a major impact on the participant's rights, safety, or well-being or the completeness, accuracy, or reliability of the study data.

### 2. Reporting and Managing Protocol Deviations

The study site principal investigator has the responsibility to identify, document and report protocol deviations as directed by the study Sponsor. However, protocol deviations may also be identified during site monitoring visits or during other forms of study conduct review.

Upon determination that a protocol deviation (major or minor) has occurred, the study staff will a) notify the site Principal Investigator, b) notify the DMCC and c) will complete a Protocol Deviation form. The Protocol Deviation form will document at a minimum the date PD occurred, the date PD identified, a description of event, whether the deviation resulted in SAE/AE, the signature of PI, report to central IRB, and documentation of a corrective action plan. The DMCC and DAIT/NIAID may request discussion with the PI to determine the effect of the protocol deviation on the study participant and his/her further study participation, the effect of the protocol deviation on the overall study, and corrective actions. The PI will complete and sign the Protocol Deviation form and submit it to the DMCC and to the central IRB, per IRB regulations. Major protocol deviations will be reported to the DSMB by the NIAID Medical Monitor at the Medical Monitor's discretion.

## 15 Ethical Considerations and Compliance with Good Clinical Practice (Quality Control and Quality Assurance)

### 1. Statement of Compliance

This clinical study will be conducted using good clinical practice (GCP), as delineated in *Guidance for Industry: E6 Good Clinical Practice Consolidated Guidance*, and according to the criteria specified in this study protocol. Before study initiation, the protocol and the informed consent documents will be reviewed and approved by the Cincinnati Children's Hospital Medical Center IRB (CCHMC IRB), which will serve as the central IRB for the study. Any amendments to the protocol or to the consent materials will also be approved by the CCHMC IRB before they are implemented.

The investigator will obtain approval to conduct the study from the appropriate regulatory agency in accordance with any applicable country and local-specific regulatory requirements prior to initiating the study. The investigator is responsible for ensuring that this protocol, the site's informed consent form, and any other information that will be presented to potential participants/parents or legal guardians (e.g. advertisements or information that supports or supplements the informed consent) are reviewed and approved by the IRB. The investigator agrees to allow the IRB direct access to all relevant documents. The IRB must be constituted in accordance with all applicable regulatory requirements. The investigator will provide the IRB with relevant document(s)/data that are needed for approval of the study.

### 2. Informed Consent Process

The consent process will provide information about the study to a prospective participant and will allow adequate time for review and discussion prior to his/her decision. The principal investigator or designee listed on the delegation log will review the consent and answer questions. The consent designee must be listed on the delegation log, have knowledge of the study and received training (from the local IRB, PI, or study coordinator) in the consent process. The prospective participant will be told that being in the trial is voluntary and that he or she may withdraw from the study at any time, for any reason. All participants (or their legally acceptable representative) will read, sign, and date a consent form before undergoing any study procedures. Consent materials will be presented in participants' primary language. A copy of the signed consent form will be given to the participant.

This study will be conducted in compliance with ICH E6 GCP: Consolidated Guidelines pertaining to informed consent. At the first visit, prior to initiation of any study-related procedures, participants will give their written consent to participate in the study after having been informed about the nature and purpose of the study, participation/termination conditions, and risks and benefits. If the participant is unable to provide written informed consent, the participant's legally acceptable representative may provide written consent as approved by institutional

specific guidelines. The informed consent document must be signed and dated by the participant, or the participant's legally authorized representative, prior to study participation. A copy of the informed consent document must be provided to the participant or the participant's legally authorized representative. Signed consent forms must remain in the participant's study file and be available for verification by the monitor, IRB, and/or regulatory authorities at any time. If participant's legally acceptable representative provides written consent, participants will also give their written assent to participate in the study as approved by institutional specific obtaining assent.

The consent form will be revised when important new safety information is available, the protocol is amended, and/or new information becomes available that may affect participation in the study.

### 15.3 Privacy and Confidentiality

A participant's privacy and confidentiality will be respected throughout the study. Each participant will be assigned a unique identification number and these numbers rather than names will be used to collect, store, and report participant information. Site personnel will not transmit documents containing protected health information (PHI) to the study sponsor or their representatives.

Although the study staff will do its best to adhere to strict privacy guidelines, the possible risk of a breach of confidentiality does exist. Every effort will be made to maintain the confidentiality of the participant's medical and research information. The investigator will take all necessary measures to keep all of the participant's personal information private and confidential. Electronic study records will be protected with electronic safeguards (e.g., computer passwords, restricted access privileges). Paper-based PHI will be secured in locked cabinets. Access to study records will be limited only to research staff. For this study, the research study staff will collect and utilize data obtained from the participant's medical and research records and observations, including laboratory tests. This information, along with the study survey forms, will be used by the Sponsor and Investigator as part of the study data. The participants will be assigned and identified by a participant study identification number. The link to the participant's study IDs and their names and identifiers will be kept by the PI and/or the research staff in a secure location. Because the participant's PHI will be collected and used for the study, the research staff will obtain a signed HIPAA authorization and informed consent from the participant and/or legal guardian. The research staff will perform informed consent and all study procedures in a private setting away from the public. In addition, the research staff will only collect the minimum amount of personal information about the participant necessary for the research study.

The PI, members of the study's research team, assigned study monitor(s), CCHMC medical staff, federal and other regulatory agencies (including the FDA), CCHMC IRB, and Office of Research Compliance and Regulatory Affairs, and DSMB will be have access to the participant's medical and research records related to this study. The data from the study may be published; however, the participant will not be identified by name.

#### 15.4 Certificate of Confidentiality

This research is covered by a Certificate of Confidentiality from the National Institutes of Health. The researchers with this Certificate may not disclose or use information, documents, or biospecimens that may identify the participant in any federal, state, or local civil, criminal, administrative, legislative, or other action, suit, or proceeding, or be used as evidence, for example, if there is a court subpoena, unless the participant has consented for this use. Information, documents, or biospecimens protected by this Certificate cannot be disclosed to anyone else who is not connected with the research except, if there is a federal, state, or local law that requires disclosure (such as to report child abuse or communicable diseases but not for federal, state, or local civil, criminal, administrative, legislative, or other proceedings, see below); if the participant consents to the disclosure, including for their medical treatment; or if it is used for other scientific research, as allowed by federal regulations protecting research participants.

The certificate cannot be used to refuse a request for information from personnel of the United States federal or state government agency sponsoring the project that is needed for auditing or program evaluation by the U.S. Department of Health and Human Services and/or the National Institutes of Health, which is funding this project or for information that must be disclosed in order to meet the requirements of the Federal Food and Drug Administration (FDA). The Certificate of Confidentiality does not prevent a participant from voluntarily releasing information about themselves or their involvement in this research. If a participant wants to release information released to an insurer, medical care provider, or any other person not connected with the research, the participant must provide consent to allow the researchers to release it.

Even with the Certificate of Confidentiality the investigators continue to have ethical obligations to report child abuse or neglect and to prevent an individual from carrying out any threats to do serious harm to themselves or others. If keeping information private would immediately put the study participant or someone else in danger, the investigators would release information to protect the participant or another person. The Certificate of Confidentiality will also not be used to prevent disclosure as required by federal, state, or local law, such as reports of child abuse and neglect, or harm to self or others.

### 16 Investigator Requirements

#### 16.1 Protocol Adherence

The investigator must adhere to the protocol as detailed in this document and agree that the Sponsor and the IRB must approve any change to the protocol. The investigator will be responsible for enrolling only those participants who have met the protocol screening and study entry criteria.

## 2. Case Report Forms

The CRFs will be used for the recording of all information and study data as specified by this protocol. The CRFs must be completed by the research personnel. The principal investigator is responsible for ensuring that accurate CRFs are completed in a timely manner. Collected data will be entered into online electronic case report forms. Electronic case report forms will be developed in collaboration with the Data Management and Coordinating Center that contain the requisite data fields.

## 3. Source Document Maintenance

Source documents are defined as the results of original observations and activities of a clinical investigation. Source documents may include, but are not limited to, study progress notes, e-mail correspondence, computer printouts, clinical laboratory data, and recorded data from automated instruments. All source documents produced in this study will be maintained by the investigator and made available for inspection by regulatory authorities. The original signed dated informed consent form for each participating participant shall be filed with records kept by the investigator and a copy given to the participant. The patient outcome questionnaires will be recorded directly on the paper forms and will be considered as source data.

## 4. Inspection of Records

Data generated by this study must be available for inspection by any regulatory authorities and the IRB as appropriate. At a participant's request, medical information may be given to his or her personal physician or other appropriate medical personnel responsible for his or her welfare. Participant medical information obtained during the course of this study is confidential and disclosure to third parties other than those noted above is prohibited.

